4.2.4.4 Biomarker Research

Immunotherapy as a target in MPN has not been extensively studied. As such, an important component of this study will be to gain better understanding of markers that predict outcome and response to PD-1 therapy.

1. Biomarker: Assess expression of PD-1/PD-L1 on peripheral blood PB-MNCs, T-cells and CD34+cells by flow cytometry:

Up-regulated PD-1 expression on peripheral blood MNCs and PD-L1 on MPN CD34+cells provides an inappropriate immune tolerance signal allowing for disease progression. Pre-clinical data suggests that PD-1 and PD-L1 are upregulated in patients with MDS and AML, especially in those who have received prior treatment. As part of this clinical trial we will test PD-1 and PD-L1 expression in circulating T-cells and tumor cells, respectively, to evaluate if expression of these molecules correlates with disease status and response to treatment.

Expected result: PD-1 expression is up-regulated on PB MNC and T-cells and PD-L1 is up-regulated on MPN HSC from patients enrolled on this trial at baseline.

Assay: Expression of PD-1 and PD-L1 will be measured by flow cytometry on cells from the peripheral blood of treated patients at baseline and at the start of cycle 3 (9 weeks).

2. Biomarker: Assess expression of PD-1/PD-L1 on bone marrow CD34+cells and supporting stromal cells by immunohistochemical staining

Up-regulated PD-1 expression on peripheral blood MNCs and PD-L1 on MPN CD34+cells provides an inappropriate immune tolerance signal allowing for disease progression. Pre-clinical data suggests that PD-1 and PD-L1 are upregulated in patients with MDS and AML, especially in those who have received prior treatment. As part of this clinical trial we will test PD-1 and PD-L1 expression in circulating T-cells and tumor cells, respectively, to evaluate if expression of these molecules correlates with disease status and response to treatment. Expression of CD45 surface marker will be evaluated in parallel with PD-1 and/or PD-L1 expression to differentiate between stromal (CD45 positive) and hematopoietic cells (CD45 positive) within the bone marrow.

Expected result: PD-1 expression is up-regulated on PB MNC and T-cells and PD-L1 is up-regulated on MPN HSC from patients enrolled on this trial at baseline.

Assay: Expression of PD-1 and PD-L1 will be measured by immunohistochemistry on bone marrow.

3. Biomarker: Assess PD-1/PD-L1 DNA methylation status by bisulfite-sequencing assay

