Changes in gene methylation status correlate with protein expression. Little is known about the significance of methylation status and PD-1/PD-L1 expression in MPN. Differences in methylation status in MDS have been used to characterize different MDS risk groups as a result of epigenetic dysregulation.

Assay: We will measure PD-1/PD-L1 gene methylation status by bisulfite-sequencing assay.

Expected result: Differential methylation will correlate with expression levels of PD-1/PD-L1, which in turn will correlate with disease status and response to PD-1 antibody therapy. These results will be instrumental in determining treatment strategies after hypomethylating agent failure in MPN-AP/BP based on their PD-1 expression status and additionally may suggest a role for hypomethylating agent priming prior to PD-1 inhibition in MF-CP patients.

4. Biomarker: Assess status and change in PD-1/PD-L1 expression with response to therapy.

PD-1/PD-L1 expression has been investigated in a variety of malignancies as biomarkers of response to therapy, little is known about the significance of PD-1 and PD-L1 expression in MPN and if these markers are surrogates for disease response.

Expected result: Changes in PD-1 and PD-L1 expression, as measured in exploratory aims 1-3, will correlate with disease response assessed by conventional response criteria (IWG-ELN).

5. Biomarker: Assess changes in driver mutation burden (*JAK2V617F*, *MPLW515L/K*, *CALR*) in granulocytes from treated patients at diagnosis, after 6 cycles and at 1 year of pembrolizumab therapy and correlate with response to therapy.

Changes in mutational status allele burden may correlate with disease response. In addition, it is unknown if patients with different mutations will respond preferentially to PD-1 therapy. We will correlate mutational status as well as change in allele burden with disease status and response to therapy and with expression of PD-1 and PD-L1.

Expected Result: Driver mutation burden will decrease in response to pembrolizumab therapy.

Assay: In order to assess changes in driver mutation burden we will use the rapid heme panel for next generation sequencing at Brigham and Women's hospital.

6. Biomarker: Evaluate changes in Immune response gene expression profile as well as tumor microenvironment in bone marrow biopsy specimens using nanostring technology after 6 cycles of treatment with pembrolizumab

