5.8 Subject Withdrawal/Discontinuation Criteria

Subjects may withdraw consent at any time for any reason or be dropped from the trial at the discretion of the investigator should any untoward effect occur. In addition, a subject may be withdrawn by the investigator or the Sponsor if enrollment into the trial is inappropriate, the trial plan is violated, or for administrative and/or other safety reasons. Specific details regarding discontinuation or withdrawal are provided in Section 7.1.4 – Other Procedures.

A subject must be discontinued from the trial for any of the following reasons:

- The subject or legal representative (such as a parent or legal guardian) withdraws consent.
- Unacceptable adverse experiences as described in Section 5.2.1.2
- Subject did not achieve at least a CI response per Table 5 for the MF-CP cohort or at least PR for the MPN-AP/BP cohort per Table 6A at response assessment.

- Intercurrent illness that prevents further administration of treatment
- Investigator's decision to withdraw the subject
- The subject has a confirmed positive serum pregnancy test
- Noncompliance with trial treatment or procedure requirements
- The subject is lost to follow-up
- Administrative reasons

The End of Treatment and Follow-up visit procedures are listed in Section 6 (Protocol Flow Chart) and Section 7.1.5 (Visit Requirements). After the end of treatment, each subject will be followed for 30 days for adverse event monitoring (serious adverse events will be collected for 90 days after the end of treatment as described in Section 7.2.3.1).

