^f Comprehensive Serum Chemistry Panel should include the following: Albumin, Alkaline phosphatase, Glucose, Alanine aminotransferase (ALT), Aspartate aminotransferase (AST), Lactate dehydrogenase (LDH), (CO₂ or bicarbonate), Uric Acid, Calcium, Chloride, Glucose, Phosphorus, Potassium, Sodium, Magnesium, Total Bilirubin, Direct Bilirubin (If total bilirubin is elevated above the upper limit of normal), Total protein, Blood Urea Nitrogen

^g Flow cytometry for acute leukemia panel and cytogenetics will be sent from the bone marrow aspirate, if this is not obtainable then will be sent from the peripheral blood to be performed locally at study site

^h If it is known, prior to C7D1, that the patient will not achieve the required response, CI, for continuation, the C7D1 and End of Treatment visit will be combined. All study activities for C7D1 will be done except dosing of the study medication.

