8.2.4.3 Biomarker: Assess PD-1/PD-L1 DNA methylation status by bisulfite-sequencing assay

To assess PD-1/PD-L1 DNA methylation status geometric means of PD-1/PD-L1 methylation levels (expressed as percentage) will be reported at baseline and at the start of cycle 3. The change in geometric mean methylation levels from baseline to start of cycle 6 will be reported as the ratio of geometric means and tested for difference from one using a paired t-test on log transformed data.

8.2.4.4 Biomarker: Assess status and change in PD-1/PD-L1 expression with response to therapy.

To assess status and change in PD-1/PD-L1 expression with response to therapy, the proportion of patients responsive to treatment following their 6th cycle will be computed and compared between PD-1/PD-L1 positive and negative patient groups, with positivity based on 3rd cycle expression levels, using a Fisher's exact test of association.

8.2.4.5 Biomarker: Assess changes in driver mutation burden (*JAK2V617F*, *MPLW515L/K*, *CALR*) in granulocytes from treated patients at diagnosis, after 6 cycles and at 1 year of pembrolizumab therapy and correlate with response to therapy.

To assess the correlation between changes in driver mutation burden from diagnosis to 1 year of pembrolizumab therapy and response to therapy, the median *JAK2V617F*, *MPLW515L/K* and *CALR* allele burden (expressed as a percentage) will be computed at baseline, after 6 cycles of treatment and at 1 year, with significant changes from baseline evaluated using the Wilcoxon signed rank test at each of the two follow-ups. Among patients positive for each mutation, a linear mixed-effects model will be fit to log-transformed allele burden data with

Product: MK-3475

Protocol/Amendment No.:

patient as the random effect and time points as the fixed effect. The mean changes from baseline in PD-1 and PD-L1 and their standard errors will be derived at each time point from the model.

8.2.4.6 Biomarker: Evaluate changes in Immune response gene expression profile as well as tumor microenvironment in bone marrow biopsy specimens using nanostring technology after 6 cycles of treatment with pembrolizumab.

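### Two exploratory analyses cannot be run as written: 8.2.4.5 never uses response and reports a variable outside its model, and the cycle 3 positivity in 8.2.4.4 has no applicable cut-off

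*Combined protocol and SAP*

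**What the plan says.** **Driver mutation burden (8.2.4.5).** The aim is stated as "To assess the correlation between changes in driver mutation burden from diagnosis to 1 year of pembrolizumab therapy and response to therapy". The methods are median allele burden at three time points, signed-rank tests of each follow-up against baseline, and a model: "Among patients positive for each mutation, a linear mixed-effects model will be fit to log-transformed allele burden data with" "patient as the random effect and time points as the fixed effect". The section closes with "The mean changes from baseline in PD-1 and PD-L1 and their standard errors will be derived at each time point from the model".

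Section 4.2.4.4 describes "an important component of this study will be to gain better understanding of markers that predict outcome and response to PD-1 therapy". For driver mutations it also plans to correlate mutational status "as well as change in allele burden with disease status and response to therapy and with expression of PD-1 and PD-L1".

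**Expression and response (8.2.4.4).** The proportion responding after cycle 6 is compared by Fisher's exact test between PD-1/PD-L1 positive and negative patients, with positivity taken from cycle 3. The only definition of positivity is in 8.2.4.2: marrow immunohistochemistry with staining intensity of at least 2 in over 5% of tumour cells. Section 8.2.4.1 describes blood flow cytometry as fluorescence intensity and percentage of cells, and gives no level at which a patient counts as positive.

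**Sampling.** Table 8 collects blood for flow cytometry at baseline, start of cycle 3, end of cycle 6, and end of cycle 12 or end of study. It shows no marrow at cycle 3. The flow chart places marrow at screening and C7D1.

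**The concern.** Followed literally, 8.2.4.5 yields within-patient changes over time, says nothing about response, and calls for a result its model cannot produce. The stated question goes unanswered, although patients give samples for it.

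In 8.2.4.4 the grouping variable does not exist until someone chooses a cut-off, an antigen (PD-1 or PD-L1) and a cell subset. The trial is open-label and response becomes known as data accrue, so those choices could be made with the response results in view. Section 8.2.4.4 also aims at change in expression, and no analysis of change by response is given anywhere in 8.2.4.

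**Working it through.** The plan gives no power, alpha or sample size for these exploratory analyses, so there is no stated figure to reproduce.

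**1. Does response enter 8.2.4.5?**

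| Element | Outcome | Terms | Response used? |
|---|---|---|---|
| Signed-rank tests | allele burden | follow-up v baseline | no |
| Mixed model | log allele burden | patient (random), time (fixed) | no |
| Stated output | PD-1 and PD-L1 change | in neither analysis | no |

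One simulated data set illustrates this: 20 patients, 6 responders, true log changes of −0.5 and −0.8 in responders only. The time-only model should return about (6/20)×(−0.5) = −0.15 and (6/20)×(−0.8) = −0.24. It returned −0.12 and −0.23, with no information on response. Adding a time-by-response term gave interactions of −0.59 and −0.95.

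**2. When can the comparison be made?** Section 5.8 discontinues patients under this criterion: "Subject did not achieve at least a CI response per Table 5 for the MF-CP cohort". MF-CP non-responders therefore leave at the post-cycle-6 assessment, and later data come essentially from responders. The end of cycle 6 is the usable time point. For patients already known not to respond, footnote h of the flow chart says: "All study activities for C7D1 will be done except dosing of the study medication".

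**3. Power of that comparison.** Assumptions: full accrual of 24 MF-CP patients; 3 to 6 responders (3/24 = 12.5%, 6/24 = 25%); normal data with unit SD; exact rank-sum test at two-sided 0.05; all drivers pooled; 40,000 simulations.

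| Responders v non-responders | 1 SD | 1.5 SD |
|---|---|---|
| 3 v 21 | 0.28 | 0.55 |
| 6 v 18 | 0.49 | 0.83 |
| 3 v 13 (only 16 pairs, assumed) | 0.24 | 0.49 |
| 6 v 10 (only 16 pairs, assumed) | 0.38 | 0.72 |

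These are for a pooled test. The plan works per driver mutation, where groups are smaller and power is lower.

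**4. What the missing cut-off does to the Fisher test.** With 24 patients and 3 responders, the smallest attainable p depends on how many patients are called positive:
- 3 positive: 1/C(24,3) = 1/2024 = 0.0005
- 6 positive: C(6,3)/2024 = 20/2024 = 0.0099
- 8 positive: C(8,3)/2024 = 56/2024 = 0.028
- 12 positive: 2×C(12,3)/2024 = 440/2024 = 0.217

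So the cut-off decides whether the test can reach 0.05 at all.

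Under no association (20,000 permutations, one antigen, cut-offs leaving at least 3 patients per group), the proportion of data sets with p≤0.05 is:

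| Responders | Best cut-off | Fixed median split |
|---|---|---|
| 3 | 0.127 | 0 |
| 4 | 0.109 | 0 |
| 5 | 0.172 | 0.038 |
| 6 | 0.149 | 0.014 |

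Exact check of the median split: for 5 responders, 2×C(12,5)/C(24,5) = 1584/42504 = 0.037; for 6, 2×C(12,6)/C(24,6) = 1848/134596 = 0.014.

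**5. Visit labels.** With 3-week cycles, the start of cycle 6 is week 3×5 = 15 and C7D1 is week 3×6 = 18. Week 15 is named in the flow summary (8.2.4.1), McNemar's test (8.2.4.2) and the methylation test (8.2.4.3), but no correlative sample is scheduled then. Section 8.2.4.2 also summarises H-scores after cycle 2, when no marrow is taken. Methylation is summarised at the start of cycle 3 but tested at cycle 6.

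**The case against.** These endpoints are exploratory and the plan claims no error control for them. A competent analyst would probably read the last sentence of 8.2.4.5 as a slip for allele burden. That is a fair guess, but it does not put response into the analysis. Nor does the sentence deliver the correlation of burden with PD-1/PD-L1 expression planned in 4.2.4.4, because expression is not in the model.

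Four stronger readings are tempting and the documents do not support them.

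- **That McNemar's test and the methylation test would be lost for want of a sample.** Neighbouring change tests use the end of cycle 6, and Table 8 and the flow chart schedule that sample. The start of cycle 6 is most likely a label slip. Only methylation is truly ambiguous, because blood exists at both cycle 3 and the end of cycle 6.
- **That the plan carries an 11–17% false-positive rate.** It states one Fisher test and proposes no search over cut-offs. The range is a worst case. The 0–4% comparator is low largely because Fisher's test is conservative at these sizes.
- **That change in expression is never analysed.** Sections 8.2.4.1 and 8.2.4.2 test change from baseline to the end of cycle 6. What is missing is change by response.
- **That the power figures describe the per-driver analysis.** They describe a pooled test with the stated numbers of complete pairs.

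Full accrual is also not assured. The chance of no response among the first 9, which ends the trial, is 0.95^9 = 0.63 at a 5% response rate, 0.875^9 = 0.30 at 12.5% and 0.75^9 = 0.08 at 25%.

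**Conclusion.** The point holds for two analyses. Section 8.2.4.5 cannot answer its own question and names an output its model cannot give; this follows from the text and needs no assumption. Section 8.2.4.4 depends on a cycle 3 classification for which the plan has no applicable rule; this too is textual.

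The consequences are conditional. The worst-case 11–17% assumes 24 evaluable patients, 3 to 6 responders, one antigen and an unrestricted search. The burden-by-response comparison is low-powered even when correctly specified: 0.28 to 0.49 for a 1-SD difference with 24 complete pairs pooled over drivers. The visit labels are editorial.

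The change should be made because it is cheap and the plan itself gives these markers weight. Nothing here touches the primary endpoint, the Simon rule or the safety rules.

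**What to change.** **8.2.4.5.** Name change in allele burden as the model output. Add a pre-specified comparison of change in burden from baseline to the end of cycle 6 between MF-CP responders and non-responders, using either a time-by-response term or a rank-sum test. Label it exploratory and low-powered, say whether it is per driver or pooled, and list individual values where a driver group is small. Either give a method for the correlation with PD-1/PD-L1 expression planned in 4.2.4.4, or drop it.

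**8.2.4.4.** Before response data are examined, fix the flow cytometry cut-off, antigen and cell subset for the cycle 3 blood sample. Alternatively, use baseline marrow positivity, for which 8.2.4.2 already has a rule; the antigen must still be named, and the question becomes one about baseline status. Add a comparison of change in expression by response.

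**Editorial.** Change the start of cycle 6 (8.2.4.1 to 8.2.4.3) and the post-cycle-2 summary (8.2.4.2) to the end of cycle 6 (C7D1). Make the methylation summary and its test refer to the same visit.

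**Cost.** SAP wording and, if the flow option is kept, one pre-set cut-off. The baseline, cycle 3 blood and C7D1 samples are already scheduled, so no added sampling is needed.

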8.3 Interim Analysis

In addition to periodic safety monitoring, a formal interim analysis will be performed after 9 patients (from the primary cohort) have been assessed at the post cycle six assessments or at the time of withdrawal for those patients not completing six cycles of treatment. If at least one response is observed after six cycles of treatment, 15 additional patients will be accrued in the second stage. If no responses are observed the trial will be terminated.

8.4 Sample Size Calculation

Refer to Section 4.2.3: Study Design and Statistical Methods.

9.0 LABELING, PACKAGING, STORAGE AND RETURN OF CLINICAL SUPPLIES

9.1 Investigational Product

The investigator shall take responsibility for and shall take all steps to maintain appropriate records and ensure appropriate supply, storage, handling, distribution and usage of investigational product in accordance with the protocol and any applicable laws and regulations.

Clinical Supplies will be provided by Merck as summarized in Table 7.

Table 7. Product Descriptions

Product: MK-3475

Protocol/Amendment No.:

Product Name & Potency	Dosage Form
Pembrolizumab 50 mg	Lyophilized Powder for Injection
Pembrolizumab 100 mg/ 4mL	Solution for Injection

9.2 Packaging and Labeling Information

Clinical supplies will be affixed with a clinical label in accordance with regulatory requirements.

9.3 Clinical Supplies Disclosure

This trial is open-label; therefore, the subject, the trial site personnel, the Sponsor and/or designee are not blinded to treatment. Drug identity (name, strength) is included in the label text; random code/disclosure envelopes or lists are not provided.

9.4 Storage and Handling Requirements

Clinical supplies must be stored in a secure, limited-access location under the storage conditions specified on the label.

Receipt and dispensing of trial medication must be recorded by an authorized person at the trial site.

Clinical supplies may not be used for any purpose other than that stated in the protocol.

9.5 Returns and Reconciliation

The investigator is responsible for keeping accurate records of the clinical supplies received from Merck or designee, the amount dispensed to and returned by the subjects and the amount remaining at the conclusion of the trial.

Upon completion or termination of the study, all unused and/or partially used investigational product will be destroyed at the site per institutional policy. It is the Investigator's responsibility to arrange for disposal of all empty containers, provided that procedures for proper disposal have been established according to applicable federal, state, local and institutional guidelines and procedures, and provided that appropriate records of disposal are kept.

10.1 Compliance with Trial Registration and Results Posting Requirements

Under the terms of the Food and Drug Administration Modernization Act (FDAMA) and the Food and Drug Administration Amendments Act (FDAAA), the Sponsor of the trial is solely responsible for determining whether the trial and its results are subject to the requirements for submission to the Clinical Trials Data Bank, <http://www.clinicaltrials.gov>. Information posted will allow subjects to identify potentially appropriate trials for their disease conditions and pursue participation by calling a central contact number for further information on appropriate trial locations and trial site contact information.

10.2 Quality Management System

10.3 Data Management Plan

10.4 ELECTRONIC Data CAPTURE (edc) SYSTEM

All computerized data entry will be performed by the Sponsor's representative. All CRFs will be logged electronically and the data entered into a web-based electronic research application portal known as eRAP. eRAP's role-based access control security and audit capability ensures that the research data is protected from unauthorized access, modification, and exposure. Key features of this web-based database system include allowing access and data entry from multiple sites, with each site having a separate pool of data as necessary. All data stored in the eRAP system is backed up daily. Detailed audit services include any data field level changes, who made the changes, when the changes were made, the old value and the new value. Data from eRAP can easily be extracted to excel or flat text file formats for easy import into SAS or other statistical software packages.

11.0 DATA AND SAFETY MONITORING PLAN

The site principal investigator (PI) will be responsible for ensuring participants' safety on a daily basis. The Data and Safety Monitoring Board (DSMB) will act in an advisory capacity to monitor participant safety, evaluate the progress of the study, to review procedures for

Product: MK-3475

Protocol/Amendment No.:

maintaining the confidentiality of data, the quality of data collection, and data management and analyses for all subjects.

